The hypothesis is that a multidisciplinary rehabilitation program induces clinically significant and long-term improvements in the disability, pain and quality of life of workers with chronic neck pain and that these would be maintained in the long term.

3. Objectives of the study

Primary objective: to verify the efficacy of a multidisciplinary program in inducing clinically meaningful and long-term improvements through changes in scores in disability assessment scales (Neck Disability Index, Tampa scale of Kinesiophobia, Pain Catastrophising Scale), in pain (Numeric Rating Scale) and in the quality of life (Short Form-36 Health Survey) of workers suffering from chronic neck pain.

Secondary objective: to evaluate changes in work discomfort (Work Ability Index, Anamnestic survey of the upper limbs and spine's pathologies) linked to the condition of chronic neck pain.

4. Methods

A randomized, parallel-group superiority-controlled trial will be conducted in a secondary care rehabilitation hospital and approved by the hospital's Institutional Review Board (ID: PG/2020/16818; date of approval: 30 september 2020).

a) Participants

The inclusion criteria will be a diagnosis of non-specific chronic neck pain (i.e. a documented history of pain lasting >3months), a good understanding of Italian and an age of >18years.

The exclusion criteria will be acute and subacute neck pain, cognitive impairment and all causes of specific neck pain (i.e. previous spinal surgery, deformity, disc herniation, infection, fracture, myelopathy or malignancy, whiplash injuries, and systemic or neuromuscular diseases) ruled out by means of case histories and imaging. Any subjects who had previously received cognitive-behavioural therapy will be also excluded.

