Outpatients visiting the hospital between September 2020 and December 2021 will be evaluated by two physiatrists coordinated by the principal investigator. Those who meet the inclusion criteria will be asked to declare their willingness to comply with any treatment option, to which they will be randomly assigned. Once the patient gave their consent, the biostatistician will randomize the subject to one of the two treatment programmes using a permuted-block randomization procedure. The list of treatment codes will be previously generated and stored in Matlab and an automatic assignment system, also developed in Matlab, will be used to conceal the allocation. The principal investigator obtaining and assessing the data and the biostatistician making the analyses will be blinded to treatment allocation. The physiotherapists, the psychologist and the patients will not be blinded.

b) Interventional programmes

Interventions will be delivered by a psychologist and two equally experienced physiotherapists, separately responsible for the multidisciplinary and the general exercise group. Each participant will be evaluated individually by means of postural observation, cervical range of motion examination, manual muscle testing. Based on this evaluation, the exercises will be planned and carried out for each patient. Given that the Italian National System allows for 10 rehabilitative sessions for outpatients and owing to the complex nature of chronic complaints, the physiotherapists will arrange one 60-minute session of physical training per week for ten weeks and will ask the patients to repeat the exercises at home. The multidisciplinary group will meet with the psychologist once a week for a 60-minute session as described below. Thus, the multidisciplinary programme will last for a total of 20 hours, while the general exercise programme will last for 10 hours.

c) Multidisciplinary group

Multimodal exercises will be first introduced to improve, by means of graded exposure, cervical mobility, postural control, strengthening muscles and stretching the neck. Patients will learn stabilizing techniques for neck deep muscles, progressively increasing the speed and complexity of the movements. Subsequently, task-oriented exercises while maintaining spinal deep muscle activation will be introduced. Under the supervision of the psychologist, subjects will also be involved in group-based cognitive-behavioural therapy aimed at

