modifying fear of movement and maladaptive illness behaviour. The situations to handle will be identified on the basis of the fear-avoidance beliefs emerging from the group discussion of the activities more frequently reported, the administered questionnaires and the presentation of images showing neckstressing activities.

d) General exercise group

General physiotherapy will include exercises for muscle strengthening, regional stretching and spinal mobilization.

e) Both groups

Ergonomic advice was provided by means of a booklet given to the participants during the first session in order to facilitate the modification of daily living activities. At the end of treatment, patients were asked to continue with the exercises at home. A fidelity check, based on a manual including the complete list of exercises to be delivered, will be conducted at the end of each session to verify that all of the planned exercises will be actually performed.

No other treatments (e.g. physical modalities, nerve blocks, pharmacological agents) will be offered. Family doctors will be asked to avoid referrals for other treatments while the participants will be undergoing the programmes.

f) Type of data collected

- Demographic, anthropometric and clinical characteristics of the participants
- Disability (primary outcome): assessed using the validated Italian version of the self-reported 10-item Neck Disability Index (13).
- Kinesiophobia: assessed using the validated Italian 13-item version of the self-report Tampa Scale for Kinesiophobia (14).
- Catastrophizing: evaluated by means of the 13-item validated Italian version of the self-reported Pain Catastrophizing Scale (15).
- Pain intensity: assessed using an 11-point numerical rating scale (16).
- Quality of life was assessed using the Italian version of the self-report Short-Form Health Survey (17,18).
- Work ability: assessed using Work Ability Index (19).

- Anamnestic and clinical evaluation of the pathologies affecting the upper limbs and spine (20).

The questionnaires will be completed before treatment, ten weeks later (posttraining), and 12 months after the end of treatment (follow-up). At the end of treatment, the subjects will be also asked to rate the effectiveness of the treatment using the 5-point Likert Global Perceived Effect scale (21). Using a specific form, patients were asked to report any symptoms they experienced during the study that required further treatment.

5. Sample size and statistical analysis

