The sample size will be computed using the Italian Neck Disability Index, for which it will be estimated that a between-group difference of 7 points should be considered as clinically important (22). In order to assure 80% statistical power and 5% type I error, and considering a standard deviation of 15.4 points, 154 patients will be required, but 170 will be recruited to allow for a drop-out rate of 10%. The differences between the two groups relating to measures with non-normal distribution will be analyzed by Mann-Whitney U test. The null hypothesis will be rejected for p values > 0.05 (two-tailed test).

References

- 2) Hudes K. The Tampa Scale of Kinesiophobia and neck pain, disability and range of motion: A narrative review of the literature. *J Can Chiropr Assoc* 2011; 55(3): 222–232.

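### Section 5 specifies no use of baseline NDI in the primary analysis and plans no effect estimate with a confidence interval

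*Combined protocol and SAP*

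**What the plan says.** The comparison plan in Section 5 is two sentences: a test and a two-tailed p-value rule. The test sentence is "The differences between the two groups relating to measures with non-normal distribution will be analyzed by Mann-Whitney U test". No method is named for measures judged normal, no baseline term or change score is attached to any outcome, and no effect estimate or interval is mentioned.

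Other parts of the document bear on the point without filling the gap:

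- Section 3 states that efficacy will be verified "through changes in scores in disability assessment scales", with the NDI listed first.
- Section 4 f) makes the NDI the primary outcome and schedules it before treatment, at ten weeks, and 12 months after treatment ends.
- Section 5 bases the sample size on the view that "a between-group difference of 7 points should be considered as clinically important" and, "considering a standard deviation of 15.4 points, 154 patients will be required". It does not say whether that SD belongs to a score or to a change.
- Section 4 a) says that "the biostatistician making the analyses will be blinded to treatment allocation".

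**The concern.** The baseline NDI will be collected on every patient, and the objective speaks of change, but the analysis section does not say whether the comparison will use follow-up scores, change scores or follow-up scores adjusted for baseline. These are three different analyses with different power. If the choice stays open until the data are in, several p-values are available for one question.

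The second gap concerns interpretation. The trial is sized on 7 NDI points, described as clinically important, but a Mann-Whitney p-value gives no effect in NDI points to set beside that 7. The stated hypothesis is of clinically significant improvement, so the size of the difference and its uncertainty are the results a reader will need.

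**Working it through.** **Inputs.** Difference 7, SD 15.4, 80% power, two-sided 5% and 154 patients are from Section 5. The allocation ratio is not stated; 1:1 is assumed, so 154/2 = 77 per arm. The correlation r between baseline and follow-up NDI is not given; 0.3, 0.5 and 0.7 are assumed, with equal SDs at both times and in both arms.

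**1. The plan's own figure.** For a two-sample t-test the standard error is 15.4 × √(2/77) = 2.48 and the noncentrality is 7/2.48 = 2.82. The noncentral t distribution gives power 80.0% at 77 per arm and 79.5% at 76. So 154 is exactly the t-test size for a 7-point difference in means. The calculation cannot show whether those are means of scores or of changes.

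**2. Power by analysis, if 15.4 is a score SD.** Change SD = 15.4 × √(2(1−r)). ANCOVA residual SD = 15.4 × √(1−r²).

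| r | Follow-up only: SD, power | Change score: SD, power | ANCOVA: SD, power |
|---|---|---|---|
| 0.3 | 15.40, 80.0% | 18.22, 65.9% | 14.69, 83.6% |
| 0.5 | 15.40, 80.0% | 15.40, 80.0% | 13.34, 89.9% |
| 0.7 | 15.40, 80.0% | 11.93, 95.1% | 11.00, 97.5% |

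**3. Power by analysis, if 15.4 is a change SD.** Score SD = 15.4/√(2(1−r)). ANCOVA residual SD = 15.4 × √((1+r)/2).

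| r | Follow-up only: SD, power | Change score: SD, power | ANCOVA: SD, power |
|---|---|---|---|
| 0.3 | 13.02, 91.2% | 15.40, 80.0% | 12.42, 93.5% |
| 0.5 | 15.40, 80.0% | 15.40, 80.0% | 13.34, 89.9% |
| 0.7 | 19.88, 58.4% | 15.40, 80.0% | 14.20, 86.0% |

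Which of follow-up and change does better depends on r and on the meaning of 15.4. ANCOVA is above both in every row and never below 83.6%.

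**4. Cost of the rank test itself.** On normal follow-up scores, Mann-Whitney has about 78% power against 80% for the t-test. That loss of about 2 points is small beside the spread in the tables.

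**5. Type I error if the choice is left open.** In simulation (20,000 null trials per scenario; normal scores and gamma scores with skewness 1.0 and 1.4; the same r values), each single test had 4.6-5.3%. Taking the smallest p-value of four tests (t or Mann-Whitney, on follow-up or change) at one visit gave 10.4-13.0%. A separate simulation split this. A free choice of t or Mann-Whitney on follow-up scores alone gave 5.8-6.9%, and a free choice of follow-up or change with one test gave 8.3-9.4%. Most of the inflation comes from the open endpoint.

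**6. Precision of an estimate.** The 95% CI half-width is t × SD × √(2/77), with t about 1.976. Unadjusted at SD 15.4: 1.976 × 2.48 = 4.90 NDI points. With ANCOVA at r = 0.3/0.5/0.7: 4.68/4.25/3.50 if 15.4 is a score SD, and 3.95/4.25/4.52 if it is a change SD.

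**The case against.** The strongest defence is that the plan is terse rather than wrong. Restricting Mann-Whitney to non-normal measures, next to a t-test sample size, implies a t-test for normal ones, and the objective's reference to changes in scores signals that baseline will be used. Both points stand in part. They make the missing normal branch a minor matter, and they rule out saying that the document ignores baseline. They do not settle the analysis: the objective does not say how change is formed or compared, and the t-test reading fits follow-up and change scores equally well.

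A reader might go further and infer that the primary comparison would be biased or invalid, or that the sample size is wrong. The documents do not support this. Any of these randomised comparisons is valid if fixed in advance, and 154 reproduces. Nor does anything suggest that the test will be picked by its p-value. The 10-13% is a worst case, and Section 5 already restricts the choice by tying Mann-Whitney to non-normal measures.

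The blinding of the analyst offers less reassurance than it seems to. A two-sided p-value is the same whichever arm carries which label, so masked labels do not prevent selection of the smallest one.

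It is also fair to say that ANCOVA is a recommendation on efficiency. With skewed scores a rank test can beat it. At skewness 1.4 and r = 0.3, under a pure location shift with 15.4 as the score SD, Mann-Whitney on follow-up has 91.6% power against 83.7%. That advantage depends on the effect model. If treatment lowers scores proportionally, with the same 7-point mean difference, the order reverses: about 86% for Mann-Whitney on follow-up, 91% for the t-test and 93% for ANCOVA. The documents give no skewness or effect model by which to choose.

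**Conclusion.** The point holds as a gap in specification with a cheap and better alternative. Section 5 does not say how baseline NDI enters the primary comparison and plans no estimate with an interval. Over the assumed correlations and both readings of 15.4, power at 154 patients runs from 58% to 95% for the unadjusted analyses (follow-up or change) and from 84% to 98% for ANCOVA. These ranges rest on assumed r, equal SDs, 1:1 allocation, a true difference of 7 and normal data; they do not predict a loss in this trial. The omission is certain from the text, while the size of its effect is not. The change should be made, but the gap does not invalidate the design.

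**What to change.** For the NDI, replace the Mann-Whitney sentence in Section 5 with wording such as:

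*Whatever the observed distribution, NDI will be analysed by ANCOVA at each visit, with treatment and baseline NDI as terms. The adjusted mean difference with its 95% CI will be reported in NDI points and interpreted alongside the 7-point value, not as a test that the difference exceeds 7. A Mann-Whitney test with a Hodges-Lehmann shift and CI will be a sensitivity analysis.*

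The caution about 7 is needed because, when the true difference is 7, the lower limit exceeds 7 in only about 2.5% of trials.

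The cost is a change of wording and a little more analysis work, with no new data, visits or patients. The downside is the possible power loss to a rank test on skewed scores: 91.6 − 83.7 = about 8 points in the least favourable location-shift scenario examined, and about 1 to 2.5 points in the others where a rank test came out ahead. The sensitivity analysis keeps that result in view.

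Naming the primary visit, stating what 15.4 is the SD of, and giving a method for each other scale are separate points to settle alongside this one.

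### The rejection rule is inverted: section 5 rejects the null hypothesis when p exceeds 0.05, contradicting the 5% type I error in the same section

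*Combined protocol and SAP*

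**What the plan says.** The statement is in section 5 (Sample size and statistical analysis) of the combined protocol and SAP: "The null hypothesis will be rejected for p values > 0.05 (two-tailed test". It is not tied to a particular endpoint or test, so it covers the primary outcome (Neck Disability Index, section 4f) and every other comparison. No other section states a rejection rule.

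Two sentences earlier, the sample size paragraph opens its calculation with "In order to assure 80% statistical power and 5% type I error". Its inputs are that "a between-group difference of 7 points should be considered as clinically important" and "considering a standard deviation of 15.4 points". Its result is that "154 patients will be required", raised to 170 for drop-out.

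**The concern.** A small p value is evidence against the null hypothesis. The rule as written does the reverse: it rejects no difference when the data are compatible with it, and keeps it when the evidence against it is strong. That cannot be reconciled with the 5% type I error stated in the same section.

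Section 4 describes a superiority trial, and in such a trial the rejection rule is what turns data into a claim. If the sentence were followed literally, the decision on every test would be reversed. If it were ignored, as is more likely, the analysis would formally depart from its own protocol at the decision threshold. A prespecified rule should not depend on readers silently correcting it.

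**Working it through.** **Inputs from section 5**
- Difference to detect: 7 points on the Neck Disability Index
- Standard deviation: 15.4 points
- Type I error 5%, two-tailed; power 80%
- Stated requirement: 154 patients

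**Assumptions**
- 1:1 allocation. Section 4a gives two arms and permuted blocks but no ratio.
- A two-sample t-test for the primary outcome. Section 5 names only the Mann-Whitney U test, for non-normal measures.

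**Step 1: reproduce the plan's sample size under the conventional rule (reject when p < 0.05)**

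Normal approximation: n per arm = 2 × (1.960 + 0.842)² × (15.4/7)² = 2 × 7.85 × 4.84 ≈ 76, or 152 in total.

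Exact calculation with the noncentral t distribution:
- Standardised difference: 7/15.4 = 0.4545
- Noncentrality with 77 per arm: 0.4545 × √(77/2) = 2.82, on 2 × 77 − 2 = 152 degrees of freedom
- Power with 76 per arm: 0.7950, short of 80%
- Power with 77 per arm: 0.8003

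So 77 per arm, 154 in total, is the smallest equal allocation that reaches 80%. It matches the stated figure exactly. A one-sided 5% test would need only 120 by the normal approximation, so the design was sized for a two-sided 5% test.

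**Step 2: apply the written rule (reject when p > 0.05) to the same design**

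The written rule rejects exactly when the conventional rule does not, so each probability is one minus its conventional value.

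| True difference | Reject if p < 0.05 | Reject if p > 0.05 (as written) |
|---|---|---|
| 0 points | 0.05 | 1 − 0.05 = 0.95 |
| 7 points | 0.800 | 1 − 0.800 = 0.200 |

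A simulation of 200,000 trials with 77 per arm and SD 15.4 agrees. The proportion with p > 0.05 was 0.950 at no difference and 0.199 at a 7-point difference.

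Under the written rule, the chance of rejecting falls as the true difference grows, so the rule has neither the stated type I error nor the stated power.

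**Step 3: look for a correction elsewhere**

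There is none. Section 5 contains all of the plan's analysis text, and the rule appears once.

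**The case against.** The strongest reply is that the intention is plain. The same paragraph fixes a 5% type I error, and the sample size reproduces exactly under conventional two-sided testing, so only one reading makes sense. A biostatistician is assigned to the analysis (section 4a), and nothing suggests that the test would be run backwards. The figures 0.95 and 0.20 are simply the complements of 5% and 80%. They describe the inverted sign, not a likely effect on the trial.

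Most of this is right. The sign is very probably a typing slip, and a reversed conclusion follows only from literal application. A two-tailed rejection also carries no direction. Under a true null hypothesis the 0.95 would split about evenly, roughly 0.475 favouring each arm, so the literal rule would not declare the multidisciplinary programme superior 95% of the time.

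A fault in reading the PDF is also possible. However, the same symbol appears sensibly in the inclusion criteria (section 4a, on pain duration and age), and nothing in section 5 looks corrupted. The text has no less-than sign to compare against, so this cannot be settled from the text alone. The sponsor can check the source file.

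These points bear on tone and likely consequence. None of them makes the sentence correct or supplies a correct one elsewhere in the plan.

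**Conclusion.** The concern holds: the decision rule is wrong as written and contradicts the error rate stated in the same section. Taken literally with 77 per arm, it rejects a true null hypothesis with probability 0.95 instead of 0.05, and rejects at a true 7-point difference with probability about 0.20 instead of 0.80.

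The 0.95 holds for any test with exact 5% size. The 0.20 rests on the t-test and 1:1 allocation assumed above, and on the plan's SD of 15.4. The sample size shows that the design was built on the conventional rule, so the error is in the wording of the threshold and not in the design. It must still be corrected, because it is the only written criterion for every test in the trial.

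**What to change.** In the last sentence of section 5, replace the greater-than sign with a less-than sign, so that the rule is to reject when the two-tailed p value is < 0.05. With 77 per arm this restores a type I error of 5.0% and power of 80.0% at a 7-point difference.

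The cost is one character. The 154 patients required, the 170 to be recruited, the choice of tests and the design all stay as they are.
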